Dry Eye Questionnaire (DEQ-5) measures symptom severity over the last month. The test contains only five questions, making it one of the quickest to complete and grade. During the study will be asks patients to rate the severity of eye discomfort, dryness and wateriness each from 0 to 4, with 0 indicating "never" and 4 indicating "constantly." The patient will be asked about the intensity of the symptom, with a score of 0 meaning it is not intense at all, and a score of 5 meaning it is very intense. The total score is a number between 0 and 22.

All measurements will be taken by a trained optometrist and all instruments will be calibrated immediately prior to the study.

21. Statements of compliance

22.1 Declaration of Helsinki

The CRO/Sponsor and the Investigator ensure that all procedures described in this clinical investigation plan, data evaluation and documentation will be produced strictly according to normal clinical practice and the current version of Declaration of Helsinki.

22.2 Ethic Committee and Regulatory Authority Approvals and Any Additional Requirements

The clinical investigation plan and essential documents (ICF, etc..) will be approved by the Ethics Committees (ECs) and notified to the Ministry of Health. The approval of the clinical investigation will be obtained before the beginning of the study.

The study can begin only after full approval by the EC. Medical device will not be sent to Investigator/s before the EC.

22.3 Informed Consent

Before enrollment in the study, the Investigator will:

1. Explain, in a clear and detailed manner, the scope, the procedures and the possible consequences of the clinical investigation. The information will be given in both oral and written form.
2. Obtain signed informed consent from the potential subject before performing any of the procedures included in the observational study.
3. Assign screening number;
4. Determine subject eligibility;
5. Assignment of the study and allocation of subject clinical investigational number;
6. Generation of unique subject identifiers code that consist of the 5-digit screening number (e.g. S1001, S1002,...S10028 etc.), and, if applicable, the 4-digit subject clinical investigational number (e.g. 1001, 1002,...1028 etc.). Specifically, the first subject study number was referred to the study site.

Allocation screening number and subject clinical investigational number are separated by slashes (e.g. “S101/1001”).

If a subject withdraws from participation in the observational study, his/her unique subject identifiers code can't be reused.

Before being enrolled in the clinical investigation, the patients must have expressed their consent to participate by provide a written consent form. The information sheet and informed consent form will be prepared in the local language by the CRO and must be approved by the EC. It will include all the elements required by law according to the ICH-GCP recommendations.

In addition to the standard requirements that Investigators are obliged to observe in providing information, the following points must be covered:

- a description of the aims of the observational study and how it will be organised, in

accordance with the normal clinical practices;

- the type of treatment;
- any potential adverse events attributable to the clinical investigation treatment;
- the freedom to ask for further information at any time;
- the right of subjects to withdraw from the clinical investigation at any time without giving reasons and without compromising their further course of medical treatment;
- adequate time to answer possible questions.

Adequate time and opportunity to satisfy questions will be given to the patients and the time will be recorded.

The Investigator will be supplied with an adequate number of blank informed consent forms to be used. The forms will be signed and dated by both the Investigator and the subjects.

A copy of the signed form will be given to the patient.

To ensure medical confidentiality and data protection, the signed informed consent forms will be stored in the Investigator's study file according to the regulatory requirements.

The Investigator will allow inspection/audit of the forms by authorized representatives of the Sponsor, EC members and Competent Authorities (CA). He will confirm, by signing and dating the forms, that informed consent has been obtained. In case any new information regarding the IDs will be available during the study the subject will be contacted by the Investigator and in the case a new version of informed consent, will be prepared, submitted to the EC and after approval proposed to the subject for signature.

The Informed Consent will incorporate (or, in some cases, be accompanied by a separate document incorporating) the wording that complies with relevant data protection and privacy legislation (Regulation (EU) 2016/679 concerning the protection of individuals with regard to the processing of personal data, also GDPR).

22.4 Amendments and EC Additional Requirements

In order to obtain interpretable results, neither the Investigator nor the Sponsor will alter the clinical investigation conditions agreed upon and set out in this clinical investigation plan. Amendments should be made by mutual agreement between the Investigator and the Sponsor. Any amendment to this study clinical investigation plan must be set out in writing, giving the reasons, being signed by all concerned parties and will be sent to the EC. All amendments will be sent to the ECs.

Any amendments that may lead to increased risks and/or inconvenience to the subject must first be approved by the EC, if appropriate, and such approval in writing addressed to the Sponsor.

The amendment becomes then part of the clinical investigation plan.

Copies of all documents must be stored also by the Investigator/s. Any additional EC requirements will be followed as appropriate.

22.5 Insurance Policy

As the study is non-interventional, there is no need for insurance policies in addition to those already provided for normal clinical practice.

22. Subject Compliance

The Subjects' compliance will be monitored by study staff during visits and evaluated by the Investigator. Any subject found not to follow pre-study directions or to be non-compliant, will be withdrawn from the study. Details of the reason for removal of subjects will be recorded and reported.

23. Statistic

Sample size estimate

A previous study report baseline level of TFBUT of 6.23 ± 1.75 in patients with moderate dry eye disease. After 30 days of treatment with tear eyedrops containing hyaluronic acid 0.3%, TFBUT was 8.10 ± 2.06 s [20]. To detect a 25% of increase of TFBUT at Study Termination Visit compared to the baseline (Visit 1) (mean difference 1.56, s.d. 1.91), considering an alpha = 0.01 (two-tailed) and a power of $1 - \beta = 0.80$, 23 subjects are required (Wilcoxon signed-rank test). Taking into account an expected dropout of 20%, it is expected to enroll a total of 28 subjects.

Analysis set

All patients enrolled will be included in the safety population.

All patients enrolled having a primary post-baseline performance assessment will be included in the PP population and ITT population.

If the primary performance measurement at Visit 2 is missing, it will be imputed with the score at baseline. If the primary performance measurement at Study Termination Visit is missing, it will be imputed with the score at Visit 2, if it is not missing, or otherwise with the score at baseline.

All patients of the ITT population who did not have any major clinical investigation plan deviation will be included in the PP population.

The analysis of safety endpoints will be performed in the safety population. Analysis of performance endpoints will be performed on the ITT population. The analysis of primary endpoint will be performed on the PP population but this later will be repeated in the ITT population.

Statistical Methods

Descriptive analysis will be performed by using absolute rate, percentage and frequency tables for qualitative variables.

Normally distributed continuous data will be reported as minimum, maximum, mean and standard deviation, whereas non- normally distributed data as medians and IQR.

Categorical variables will be analyzed by using Yates-corrected chi-square test or Fisher's exact test when appropriate. The McNemar's test will be used to analyze paired nominal data. Differences in endpoints between baseline and different timepoints will be assessed using paired

Study code: 052/SI Hyalistil Bio PF Mono

t-test for normally distributed data, whereas the Wilcoxon signed-rank test will be used for non-normally distributed data.

Data distribution will be evaluated through the Kolmogorov-Smirnov test.

A p-value <0.05 will be considered statistically significant.

Analysis will be performed using SAS version 9.4 for Windows (SAS Institute Inc., Cary, NC, USA).

Primary endpoint analysis

- 25 % increase from Visit 1 (*Day 0 of treatment - baseline*) to Study Termination Visit (*Day 35 ± 4 of treatment*) of tear film break-up time with fluorescein (TFBUT)[◊] will be reported as minimum, maximum, mean, standard deviation or median and IQR. According to the data distribution, paired t-test or Wilcoxon signed-rank test will be used to test the statistical significance of the change from baseline to each time points. [Time frame: Visit 1, and Study Termination Visit].

Secondary endpoint analysis

- Changes in NEI score from baseline will be summarized as minimum, maximum, mean, standard deviation or median and IQR. Paired t-test or Wilcoxon signed-rank test will be used to test the statistical significance of the change from baseline to each timepoints. [Time frame: Visit 1, Visit 2 and Study Termination Visit].
- Change in the SANDE scores will be summarized as minimum, maximum, mean, standard deviation or median and IQR. Paired t-test or Wilcoxon signed-rank test will be used to test the statistical significance. Details of changes (i.e., difference in SANDE scores between baseline and end of treatment) will be summarized as well. [Time frame: Visit 1, Visit 2 and Study Termination Visit].
- VAS will be summarized reporting the number of patients and related percentage in each category. [Time frame: Study Termination Visit].
- Changes in TFBUT from baseline will be reported as minimum, maximum, mean standard deviation or median and IQR. Paired t-test or Wilcoxon signed-rank will be used to test the statistical significance of the change from baseline to each timepoints. [Time frame: Visit 2, and Study Termination Visit].
- Change in the BVCA scores will be summarized as minimum, maximum, mean, standard deviation or median and IQR. Paired t-test or Wilcoxon signed-rank test will be used to test the statistical significance. Details of changes (i.e., difference in BVCA scores between baseline and end of treatment) will be summarized as well. [Time frame: Visit 1, Visit 2 and Study Termination Visit].

Study code: 052/SI Hyalistil Bio PF Mono

- IGAS will be summarized reporting the number of patients and related percentage in each category. [Time frame: Study Termination Visit].
- Incidents will be coded using the last updated version of the MedDRA dictionary to give a preferred term (PT) and a system/organ class term (SOC) for each event. The number of patients who experienced at least one incident, study product-related incidents, serious incidents, and the number of patients withdrawn due to an incident will be summarized. The frequency of incidents will be presented overall, by SOC and PT, and additional grouping by severity and relationship to the observed treatment will be performed. [Time Frame: During the treatment period].
- Changes from baseline in IOP will be summarized as minimum, maximum, mean standard deviation or 18 median and IQR. Paired t-test or Wilcoxon signed-rank will be used to test the statistical significance of the change from baseline to each timepoints. [Time frame: Visit 1, Visit 2 and Study Termination Visit].
- Changes from baseline in DEQS score will be summarized as minimum, maximum, mean, standard deviation or median and IQR. Paired t-test or Wilcoxon signed-rank test will be used to test the statistical significance of the change from baseline to the study termination. [Time frame: Visit 1 and Study Termination Visit].

24. Data collection – eCRFs

An electronic data capture system will be used for this study. An electronic CRF (eCRF) is designed to collect all the data required by the clinical investigation plan and collected by the investigator for each patient.

The Investigator must ensure that the clinical data required by the clinical investigation plan, collected during the study, are carefully reported, in the eCRFs. He must also check that the data reported in the eCRFs correspond to those in the patients' source documents.

Details of eCRF completion and correction will be explained to the Investigator. If the Investigator authorizes other persons to make entries in the eCRF, the names, positions, signatures, and initials of these persons must be supplied to the Sponsor.

The Investigator or the designated personnel of their team agrees to complete all documents provided by the Sponsor at each patient's visit and complete the eCRF within 2 days from the patient's visit.

Any outstanding entries must be completed immediately after the final examination. An explanation should be given for all missing data.

The monitors must make certain that all data are completed on the eCRF and are according to source.

Before the lock of the database by the Data Management Department, the Investigator must attest

Study code: 052/SI Hyalistil Bio PF Mono

by entering his/her user's name and password:

- the authenticity of the data collected in the eCRF;
- the coherence between the data in the eCRF and those in the source documents.

The Investigator must keep source documents for each subject in the clinical investigation. All information on eCRFs must be traceable to these source documents, which are generally stored in the subject's medical file. The source documents will contain all demographic and medical information, as well as the original signed informed consent form.

The monitor, in accordance with the Sponsor's requirements, should ensure that the trial is properly conducted and documented.

The monitor checks the accuracy and completeness of eCRF entries, source documents, and other records related to the trial and notifies (monitoring report) the Sponsor of deviations from the clinical investigation plan, SOPs, GCP, and applicable regulatory requirements, taking appropriate action to prevent recurrence of identified deviations.

The monitor should submit a written report to the Sponsor after each trial- site visit or clinical investigation-related communication (monitoring report).

Reports should include a summary of what the monitor reviewed and the monitor's statements concerning the significant findings/facts, deviations and deficiencies, conclusions, actions taken or to be taken and/or actions recommended to secure compliance. The review and follow-up of the monitoring report with the Sponsor should be documented by the Sponsor's designated representative.

Any change or correction to eCRF should be dated, initialed, and explained (if necessary) and should not obscure the original entry.

The systems are designed to permit data changes in such a way that the data changes are documented and that there is no deletion of entered data (i.e. maintain an audit trail, data trail, edit trail).

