	
evaluations on both eyes of the individual patient.
 
In the case that both eyes are affected by ocular dry eye, the statistical analysis will be performed considering the eye with the lowest level of TFBUT score “worse eye”. If the level of TFBUT score at baseline is the same in both eyes, then the eye with the highest level of NEI score will be designated as the “worse eye.”
 
If the level of NEI score at baseline is the same in both eyes, then the right eye will be designated as the “worse eye.”
 
#The primary end point will be evaluated on the PP population and also in ITT population.

STATISTICS	
Sample size estimate
 
A previous study report baseline level of tear film break-up time with fluorescein (TFBUT) of 6.23 ± 1.75 at baseline, to detect a 25% increase of TFBUT at the Study Termination Visit compared to baseline (Visit 1) (mean difference 1.56, sd 1.91), with an alpha=0.01(two-tailed) and a power $(1 - \beta)$ of 0.80, 23 subjects are required (Wilcoxon signed-rank test). Considering a dropout of 20%, it is expected to enroll a total of 28 subjects.
 
Statistical analysis
 
Descriptive analysis will be performed by using absolute rate, percentage and frequency tables for qualitative variables.
 
Normally distributed data will be reported as minimum, maximum, means and standard deviations, whereas non-normally distributed data as medians and interquartile range (IQR).
 
To compare qualitative variables for not-paired data will be used the Chi-square test with Yates corrections or Fisher's exact test when appropriate and the McNemar's test for paired data.
 
Differences in endpoints between baseline and different timepoints will be assessed using paired t-test for normally distributed data, whereas the Wilcoxon signed-rank test will be used for non-normally distributed data.
 
Data distribution will be tested by using the Kolmogorov-Smirnov test. A p-value <0.05 will be considered statistically significant.
 
All the Analysis will be performed using SAS version 9.4 for Windows (SAS Institute Inc., Cary, NC, USA).
 
Analysis set
 
All patients enrolled will be included in the safety population.
 
All patients enrolled having a primary post-baseline -performance assessment will be included in the ITT population.
 
If the primary performance measurement at Visit 2 is missing, it will be imputed with the score at baseline. If the primary performance

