7. SAMPLE SIZE AND STATISTICAL POWER CONSIDERATION

A previous study reported by De-Hita-Cantalejo C, et al 2022 [3], baseline level of TFBUT of 6.23 ± 1.75 in patients with moderate dry eye disease. After 30 days of treatment with tear eyedrops containing hyaluronic acid 0.3%, TFBUT was 8.10 ± 2.06 s. To detect a 25% of increase of TFBUT at Study Termination Visit compared to the baseline (Visit 1) (mean difference 1.56, s.d. 1.91), considering an alpha = 0.01 (two-tailed) and a power of $1 - \beta = 0.80$, 23 patients are required (Wilcoxon signed-rank test). Taking into account an expected dropout of 20%, it is expected to enroll a total of 28 patients.

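### The stated 20% dropout allowance does not fit 28 enrolled and 23 required: 28 covers at most 17.9% dropout, though the effect on power is small

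*Protocol*

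**What the plan says.** Protocol section 23 (Sample size estimate) takes a change in TFBUT with "mean difference 1.56, s.d. 1.91", two-sided alpha 0.01 and power 0.80, and concludes that "23 subjects are required (Wilcoxon signed-rank test" applies. It then adds the allowance: "Taking into account an expected dropout of 20%, it is expected to enroll a total of 28 subjects". The Protocol synopsis has "Considering a dropout of 20%, it is expected to enroll a total of 28 subjects", and SAP section 7 has "Taking into account an expected dropout of 20%, it is expected to enroll a total of 28 patients". None of the three shows how 23 was turned into 28.

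Other parts of the plan bear on what a dropout does to the analysed number:

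- Protocol section 4 replaces withdrawn subjects until the total is 28. The sample-size paragraphs and the SAP do not mention replacement.
- Protocol section 23 and SAP 10.2.5 fill a missing final TFBUT with the Visit 2 value or, failing that, the baseline value.
- Protocol section 23 runs the primary analysis on the PP set and repeats it in the ITT set. SAP 8.3 puts the performance analysis on ITT, and SAP 8.4 calls the PP set supportive.
- SAP 11.2 lists missing primary data among the criteria for exclusion from the PP set.

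**The concern.** Dropout is a share of those enrolled, so the allowance is made by dividing the required number by one minus the dropout rate. The three figures given (23 required, 20% lost, 28 enrolled) fail that check. A reader who relies on the sentence will believe that 28 secures 23 evaluable patients at the expected loss, and on the plain arithmetic it does not. What is at stake is the accuracy of the size justification and the number available to the PP analysis, which the Protocol names first for the primary endpoint.

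**Working it through.** **Inputs.** Mean change 1.56 s (25% of the 6.23 s baseline is 1.5575), SD 1.91, two-sided alpha 0.01, power 0.80, required 23, dropout 20%, enrolled 28. All come from Protocol section 23 and are repeated in SAP section 7. The SD is taken as given.

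**The required 23.** A paired t calculation (noncentral t) gives 21. Dividing by the signed-rank test's asymptotic relative efficiency under normality, 3/pi, gives 21 x pi/3 = 21.99, so 22. The plan's 23 is within one patient of that and is accepted here.

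**The enrolled number.**

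- 23/(1 - 0.20) = 28.75, so 29. Check: 29 x 0.8 = 23.2.
- 23 x 1.2 = 27.6, which rounds up to 28, the stated figure. Truncating 28.75 would also give 28.
- 28 x 0.8 = 22.4, so 22 whole patients remain, one short of 23.
- Largest loss from 28 that keeps 23: 28 - 23 = 5, and 5/28 = 17.9%.

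**What the missing patient costs.** Signed-rank power at 1.56/1.91, using the 3/pi efficiency:

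| Evaluable | alpha 0.01 | alpha 0.05 |
|---|---|---|
| 21 | 77.6% | 93.4% |
| 22 | 80.3% | 94.5% |
| 23 | 82.7% | 95.4% |
| 28 | 91.5% | 98.2% |

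Simulating the exact signed-rank test with normal differences (40,000 runs) gives 80.9% at 22 and 83.1% at 23 for alpha 0.01, and 94.5% at 22 for alpha 0.05. The 0.05 column matters because Protocol section 23 and SAP section 10 set significance at p<0.05, not at the 0.01 used for sizing.

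The result depends on roughly normal differences. At the test's minimum efficiency of 0.864, power at alpha 0.01 would be 74.3% at 22 and 77.1% at 23. Neither reaches 80% there, so the choice between 22 and 23 would not decide the matter.

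**The case against.** The strongest reply is that 22 need not be the number analysed. Protocol section 4 replaces withdrawn subjects up to 28, and carry-forward keeps in the ITT analysis any dropout who has a post-baseline TFBUT. Both points stand, and they rule out an unconditional statement that 28 enrolled leaves 22.

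Replacement does not repair the sentence, however. If 28 is the total enrolled, a 20% loss leaves 22. If 28 means subjects who complete, it is not an enrolment figure with a dropout allowance built in. The text needs correcting on either reading. Nor need replacement cover every loss from the PP set: the SAP 11.2 exclusions, such as compliance that cannot be assessed, are not necessarily withdrawals.

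Two stronger readings are tempting:

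- A reader might infer that the plan applied the wrong formula, multiplying by 1.2. That is plausible, but no formula is shown and truncation gives the same 28. The mismatch does not depend on how 28 arose.
- A reader might infer that the study is underpowered. The plan's own inputs do not support this: 22 still meets the 80% target at alpha 0.01.

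**Conclusion.** The sample-size sentence is internally inconsistent in all three places. A 20% dropout with 23 required needs 29 enrolled; 28 covers at most 17.9%. The shortfall is one patient and arises only if withdrawn subjects are not replaced. It bears mainly on the PP analysis, which the Protocol puts first and the SAP calls supportive. With the stated mean change and SD and approximately normal differences, power at 22 is about 80% at alpha 0.01 and about 94% at 0.05. This is a minor correction to a stated figure and does not threaten the primary analysis.

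**What to change.** Keep 28. By the SAP's own dates (last patient last visit on 3 August 2023 in section 4, SAP version 1 on 10 October 2023 in section 1.1), a 29th patient is no longer an option in any case.

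In the Protocol synopsis, Protocol section 23 and SAP section 7, use one identical statement, either:

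- *28 enrolled allows for up to 17.9% dropout (5 of 28) while keeping 23 evaluable*; or
- *28 enrolled leaves 22 evaluable at 20% dropout without replacement, with signed-rank power of about 80% at two-sided alpha 0.01*.

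Add a clause saying whether 28 counts subjects enrolled or subjects completing, so that the statement agrees with the replacement rule in Protocol section 4. If it means completers, remove the dropout allowance from the sentence and say that the total enrolled may exceed 28.

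The cost is one or two sentences in three places, with no extra patients and no change to the analysis.
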